7.1 Recruitment and Pre-screening

The research coordination team may develop materials to aide in recruitment. This may include, but is not limited to, informational videos and brochures which provide education about erectile dysfunction and include information about the study; physician referral letter templates which can be used to promote awareness of the study in the urology community; flyers/posters which can be utilized at approved clinic locations and as part of health fair materials; templates for print advertisements which can be utilized in newsprint and media campaigns. Not all materials have been developed prior to trial initiation, however each of these recruitment methods will be reviewed and approved by the IRB prior to use.

Pre-screening of subjects includes reviewing medical records and imaging studies for inclusion/exclusions prior to consent. From the review of subjects' medical records and imaging studies on file, subjects who are determined to have a diagnosis of erectile dysfunction of organic origin, and have mild-moderate erectile function as assessed by IIEF-EF, as stated in Section 6.1, and also do not have evidence in their medical record of study exclusions stated in Section 6.2, are eligible to be consented to the study.

Investigators will inform research staff of potential participants who have been identified through pre-screening so the subjects can be approached to discuss the study and conduct the informed consent session. No study procedures will take place prior to the subjects signing of the informed consent form.

7.1.1 Waiver of Authorization for Use and Disclosure of Protected Health Information (HIPAA)

A partial waiver of HIPAA is requested for recruitment purposes only. All Protected Health Information (PHI) collected by the study investigator and/or study personnel from patient records JHS and/or UHealth will be destroyed at the earliest opportunity. All Protected Health Inform (PHI) that is acquired from JHS and/or UHealth will not be re-used or disclosed to any other person or entity, except as required by law or for authorized oversight of the research study or for other research for which the use or disclosure of PHI is permissible.

7.2 Payment to Subjects

No payments will be made to subjects as compensation for their participation in this study. The subjects will not be asked to pay for the treatments or participation in study either.

7.3 Informed Consent

7.3.1 Consenting Process

All subjects must provide written consent to participate in this study. An informed consent form (ICF) will be given to each subject. The ICF will contain all United States federally required elements, all International Conference of Harmonization of Technical Requirements for Registration of Pharmaceuticals for Human Use (ICH) required elements, and Health Insurance Portability and Accountability Act Authorization (HIPAA) information in language that is understandable to the subject. The informed consent includes descriptions of all study related procedures, all possible risks to participant, and the time commitment involved with participating. All consent forms will have IRB approval. The ICF and review must be in a form understandable to the subject. Translation of ICFs will be done in accordance with local IRB procedures.

Potential participants will be approached by one of the study investigators or research coordinators. Information regarding study participation will be provided to the potential participant prior to consent. Subjects will be given ample time to review the ICF and ask questions before signing. The Investigator or designee and the subject must both sign and date the ICF after review, and before the any study procedures are performed. The subject will receive a copy of the signed and dated form, and the original will be retained in the site study files. The research staff member obtaining consent will document the informed process in the subject's chart for monitoring purposes. The Investigator or his/her designee must emphasize to the subject that study participation is entirely voluntary and that consent regarding study participation may be withdrawn at any time without penalty or loss of benefits to which the subject is otherwise entitled.

7.3.2 Non-English Speaking Subjects

In addition to English-speaking subjects, Spanish-speakers will also be included in the trial. A certified translated version of the IRB approved English consent form will be made available to non-English speakers. Spanish version questionnaires and other patient-facing materials will also be made available.

7.4 Withdrawal Criteria

All subjects who either screen fails, is withdrawn from the study, or has completed all visits should be de-enrolled from the research database within 2 business days, in accordance with university policies (or respective institutional policy).

Subjects may be withdrawn from the study for any of the following reasons:

- a) A subject does not meet the eligibility criteria (the subject will be considered a screen failure).
- b) A subject withdraws consent.
- c) If a new treatment for erectile dysfunction is made available during the study duration, the investigator will inform the patient at a follow-up visit, and be offered withdrawal to utilize new treatment.
- d) A subject expires during protocol participation from causes other than the study treatment (not due to adverse events).
- e) At the discretion of the principal investigator for issues of non-compliance, or other behavioral factors.

8. Procedures Involved

60 men with Erectile Dysfunction (ED) of organic origin, that meet all of the inclusion and none of the exclusion criteria, will be randomized to receive either PRP+SWT, or placebo/sham in a 1:1 double-blinded fashion.

- a) Group A (30 subjects): Autologous PRP injection + SWT therapy. All subjects in this group will receive 2 sessions of autologous PRP penile injection with 30 ± 7 day treatment interval. 5mL of PRP will be injected at each session. Additionally, patients will receive a total of 3600 shocks over a five-week period, starting at initial PRP injection.
- b) Group B (30 subjects): Placebo (Normal Saline) + SHAM. All subjects in this group will receive 2 sessions of normal saline penile injection with 30 ± 7 day treatment interval. 5mL of normal saline will be injected at each session. Additionally, patients will receive SHAM treatment over a five-week period, starting at initial placebo injection.

8.1 Schedule of Events:

The events table for the conduct of this study is shown below:

Table 1:

Schedule of Events		Screening	Treatment					Follow Up	
Time Point		0-30 days before randomization	Week 1	Week 2	Week 3	Week 4	Week 5	Month 3	Month 6
Event			Day 0	Day 7 \pm 2	Day 14 \pm 2	Day 21 \pm 2	Day 28 \pm 2	Day 90 \pm 14	Day 180 \pm 14
Informed Consent		X							
Demographics		X							
Medical History		X							
Physical Exam		X							
Doppler Ultrasound		X							X
Questionnaires	IIEF	X						X	X
	EDITS							X	X
	VAS		X	X	X	X	X		
	IPSS	X							X
	SGA								X
Laboratory Tests		X							
Randomization			X						
PRP/Placebo			X				X		
Shockwave/Sham			X	X	X	X	X		
Concomitant Medications/Therapy		X	X	X	X	X	X	X	X
Review Adverse Events			X	X	X	X	X	X	X

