- 8.2.13 *PRP/Placebo Injection:*** Approximately 120mL of blood will be collected from participants for preparation of investigational product. Refer to Section 9.2 for description of IP preparation and administration.

8.2.14 Concomitant Medications: Review of current use of prescription and over the counter (OTC) medications. Participants must discontinue use of PDE5i medications throughout the duration of the study.

8.2.15 Review Adverse Events: Refer to Section 12 for description and reporting of adverse and serious adverse events.

8.2.16 SWT/Sham Treatment: In the treatment group, patients randomized will receive 5 weekly sessions, in which 720 shocks of treatment energy will be applied in every session to each treated region (left and right corpora cavernosa and crura). In the sham group, patients will have the same number of sessions, and the machine will be set to deliver 720 shock treatments, but the machine will not fire shockwaves.

8.2.17 Laboratory Testing: Hematology, chemistry, hemoglobin A1C, and serum testosterone lab test results will be collected at screening. If any standard of care labs testing have been performed within 12 months of the date of the screening visit, those results may be used for the purpose of this study.

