14.1 Data Analysis Plan

Analysis plan: Continuous data will be analyzed using ANOVA with repeated measures, or student's T-Test (where applicable) in order to compare differences between the treatment and control groups. For categorical data, Fisher's Exact test to determine differences between groups. Statistical significance will be evaluated using $\alpha=0.05$.

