14.2 Sample Size

Inclusion Criteria are men with IIEF scores >11 which includes men with mild (IIEF 16-21) and mild/moderate (12-16) Erectile dysfunction. Minimal clinically important difference (MCID) for these groups are an increase of 2 for mild and 5 for moderate ED. Previous studies on the effect of placebo show about a 15% improvement in men with mild to moderate ED. Therefore, 15% of the placebo group is expected to meet MCID. Results from the PRP safety study by Matz et al. 2018, which showed a mean improvement in IIEF of 4.14 points in seven patients with ED after PRP. In the interventional group, we expect 50% to meet MCID. At 80% power, we will therefore need 30 patients in each group to detect a difference of 35% between treatment and placebo arms.

$$\text{Sample size} = \frac{2(Z_{\alpha/2} + Z_{\beta})^2 P(1-P)}{(P_1 - P_2)^2}$$

$$24 = (2*(1.96+0.84)^2 * (0.25*(1-0.25))) / (0.35^2)$$

Assuming attrition of approximately 20%, an additional 6 participant slots will be added to each group for a total sample size of 60 subjects.

15. Risks and Benefits

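### Section 7.4 lets randomised men be withdrawn from the whole study, at the investigator's discretion or to take a new treatment, with no outcome collection afterwards, so the efficacy comparison can be biased and safety observation cut short

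*Combined protocol and SAP*

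**What the plan says.** Section 7.4 introduces its list with "Subjects may be withdrawn from the study for any of the following reasons". Two of the reasons matter here.

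- Reason (e) is "At the discretion of the principal investigator for issues of non-compliance, or other behavioral factors". Neither term is defined.
- Reason (c) covers a new ED treatment that becomes available during the study: "the investigator will inform the patient at a follow-up visit, and be offered withdrawal to utilize new treatment". This happens after randomisation and treatment.

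Section 7.4 does not distinguish stopping study treatment from ending follow-up. It also says that men who fail screening, are withdrawn or finish all visits "should be de-enrolled from the research database within 2 business days".

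The schedule in Section 8.1 places IIEF, concomitant medication and adverse-event review at Months 3 and 6. Nothing says these continue after withdrawal. The telephone call in Section 8.2.5 covers safety only, is absent from the schedule and is not tied to withdrawn men. Section 10.1 asks only that missing data be explained.

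On analysis, Section 14.1 states "Continuous data will be analyzed using ANOVA with repeated measures", or a t-test, with Fisher's exact test for categorical data. It names no analysis set and no missing-data rule. Section 14.2 meets an expected loss of about 20% by recruiting 6 more men per arm.

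**The concern.** Randomisation protects the comparison only while men stay in it, or leave for reasons unrelated to outcome. Non-compliance, behavioural reasons and interest in another treatment are all plausibly more common among men who are not improving. If those men leave and their later results are never collected, the men who remain look better than those randomised, and not necessarily to the same degree in each arm.

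The exposed results are the secondary efficacy endpoints in Section 4.2. They include the proportion reaching the MCID in IIEF-EF, on which the sample size rests. The primary endpoint in Section 4.1 is also touched: TE-SAEs are to be counted in all patients over the study period, and a man withdrawn early is observed for less of it.

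**Working it through.** **Inputs, all from Section 14.2:** MCID responders 50% active and 15% control; 24 evaluable men per arm; about 20% attrition; 30 per arm, 60 in total.

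**The plan's own figures.** 2 × (1.96 + 0.84)² × 0.25 × 0.75 / 0.35² = 24.0 per arm, and 24 / 0.80 = 30 per arm. Both reproduce with the plan's inputs.

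**Assumptions added here.** Every man lost is a non-responder, and the test uses observed cases. The documents state neither. If an arm has true responder rate p and loses a fraction d, all non-responders, the observed rate is p / (1 − d).

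*One common loss rate r among non-responders in both arms, 20% overall.* Non-responders are (0.50 + 0.85) / 2 = 67.5% of all men, so r = 0.20 / 0.675 = 29.6%.
- Active: 0.50 / (1 − 0.50 × 0.296) = 58.7%
- Control: 0.15 / (1 − 0.85 × 0.296) = 20.0%
- Difference 38.6 points, a bias of +3.6

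*Other patterns, against a true difference of 35 points:*

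| Loss | Active | Control | Difference | Bias |
|---|---|---|---|---|
| 20% in each arm | 0.50/0.80 = 62.5% | 0.15/0.80 = 18.75% | 43.75 | +8.75 |
| 20% in active only | 62.5% | 15% | 47.5 | +12.5 |
| 20% in control only | 50% | 18.75% | 31.25 | −3.75 |

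The first row needs non-responders to leave at 0.20 / 0.50 = 40% in the active arm and 0.20 / 0.85 = 23.5% in control. The one-arm rows amount to 10% loss overall, not the planned 20%.

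*No true effect.* Equal loss in both arms leaves the difference at zero. With both true rates at 32.5%, a 20% loss from one arm only gives 0.325 / 0.80 − 0.325 = 8.1 points, in either direction.

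**How far the planned loss can move a result.** Suppose 12/24 v 4/24 is observed (an invented example) with 6 men missing per arm.

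| Handling of the missing men | Counts | Difference (points) | Fisher p |
|---|---|---|---|
| Observed cases | 12/24 v 4/24 | 33 | 0.030 |
| All non-responders | 12/30 v 4/30 | 27 | 0.039 |
| Least favourable to active | 12/30 v 10/30 | 7 | 0.79 |
| Most favourable to active | 18/30 v 4/30 | 47 | 0.0004 |

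**Why no single missing-data rule settles it.** If all losses are non-responders, counting missing men as non-responders restores the true rates (0.625 × 0.80 = 0.50 and 0.1875 × 0.80 = 0.15). If the 20% loss is unrelated to response, the same rule gives 0.50 × 0.80 = 40% v 0.15 × 0.80 = 12%. That is 28 points, a bias of −7.

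**The case against.** Four stronger readings are tempting, and the documents do not support them.

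1. *Resuming a PDE5i leads to removal.* Section 8.2.14 says "Participants must discontinue use of PDE5i medications throughout the duration of the study", so a reader might infer that a man who resumes one is non-compliant and is withdrawn. No section says so, and Section 7.4 is permissive. The secondary endpoint on decreasing or discontinuing PDE5i, and the medication record at Months 3 and 6, presuppose that men taking a PDE5i are still followed. Section 8.2.14 and that endpoint conflict with each other and must be reconciled.
2. *De-enrolment removes the data.* The same sentence covers men who have completed every visit, and nothing says collected data are deleted. It reads as administrative and is not the source of the problem.
3. *Section 14.1 prescribes a completers analysis.* It is silent. Fisher's exact test can equally be run with missing results counted as failures.
4. *The comparison is biased.* It can be. Direction and size depend on who leaves which arm, which is unknown.

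Other limits also stand. Reason (c) is a voluntary offer made at a follow-up visit. Only Months 3 and 6 are scheduled, so it exposes mainly Month 6 data, and only if a new treatment appears. The 20% in Section 14.2 is attrition from all causes, so assigning it all to non-responders is a worst case. Blinding (Section 9.4) limits deliberate removal from one arm, though not losses that follow from different response in the two arms.

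None of this supplies what is missing: a requirement to keep collecting outcomes once a man is withdrawn under (c) or (e).

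**Conclusion.** The concern holds in a limited form. Followed as written, Section 7.4 can lose Month 3 and Month 6 outcomes after randomisation for reasons plausibly tied to response, and it shortens safety observation. The MCID comparison can be biased as a result. Under the stated assumptions, a common non-responder loss rate overstates the effect by 3.6 points. The patterns with a 20% loss in one or both arms run from about −4 to +12.5 points. These are illustrations, not forecasts: they assume that only non-responders leave and that observed cases are analysed. With no true effect and equal loss there is no bias. The affected efficacy endpoints are secondary, but one of them carries the sample size, and the planned loss of 6 men per arm is enough to change a conclusion. The plan should be amended.

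**What to change.** **Section 7.4.** Separate stopping study treatment from withdrawing from the study. For reasons (c) and (e), continue the already scheduled Month 3 and Month 6 IIEF, concomitant-medication and adverse-event collection unless the man withdraws consent. The clinical reasons for stopping treatment need not change.

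**Section 14.1.** Analyse all randomised men in their assigned arm. State in advance how IIEF recorded after PDE5i use or a new ED treatment is counted. Otherwise a man improved by another treatment could enter as a responder to his assigned arm. Report the MCID comparison under more than one missing-data assumption, for example missing as non-response alongside observed cases.

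**Sections 8.2.14 and 4.2.** Reconcile the PDE5i requirement with the PDE5i endpoint.

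**Cost.** A short amendment, some effort to follow men who are off treatment, and a little more analysis work. The visits are already scheduled and the stated sample size is unchanged.

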8.2 Description of Study Procedures

- 8.2.1 *Informed Consent:*** Refer to Section 7.3 for details regarding the informed consent process. Study procedures will be completed only after participants have signed the informed consent documentation.
- 8.2.2 *Demographics:*** Demographic characteristics will be recorded including: date of birth, gender, marital status, race and ethnicity.
- 8.2.3 *Medical History:*** Assessment of current and past medical, surgical, and social history will be conducted.
- 8.2.4 *Physical Examination:*** Genitourinary/Reproductive system physical exam will be performed.
- 8.2.5 *Phone Call:*** Participants will be contacted by telephone to assess safety outcomes during long term follow up.
- 8.2.6 *Doppler Ultrasound:*** Penile Doppler ultrasound will be performed as standard of care for the management of erectile dysfunction. Results from within the past 12 months can be extracted from the medical record for use in this study.
- 8.2.7 *International Index of Erectile Function (IIEF) Questionnaire:*** This validated 15-item self-evaluation scale provides pre and post treatment clinic evaluations of erectile function, orgasmic function, sexual desire, satisfaction in sexual intercourse and general satisfaction. If the subject has completed the IIEF questionnaire within the past 6 months, those results may be requested and used for the purpose of this research study. Questionnaires will be completed prior to therapy at injection visits.
- 8.2.8 *Erectile Dysfunction Inventory of Treatment Satisfaction (EDITS) Questionnaire:*** This is a psychometrically sound questionnaire used to assess satisfaction with medical treatment modalities for erectile dysfunction.
- 8.2.9 *Visual Analogue Pain Scale (VAS):*** The visual analog scale (VAS) is a validated, subjective measure for acute and chronic pain. Scores are recorded by making a handwritten mark on a line that represents a continuum between “no pain” and “worst pain”.
- 8.2.10 *International Prostate Symptom Score (IPSS):*** This eight-question screening tool used to track symptoms of benign prostatic hyperplasia (BPH)
- 8.2.11 *Subject Global Assessment (SGA):*** In this single-question survey, subjects will be asked which treatment arm they believe that they had received (placebo/sham or active therapy).
- 8.2.12 *Randomization:*** Refer to Section 9.3 for details about randomization plan
- 8.2.13 *PRP/Placebo Injection:*** Approximately 120mL of blood will be collected from participants for preparation of investigational product. Refer to Section 9.2 for description of IP preparation and administration.

8.2.14 Concomitant Medications: Review of current use of prescription and over the counter (OTC) medications. Participants must discontinue use of PDE5i medications throughout the duration of the study.

8.2.15 Review Adverse Events: Refer to Section 12 for description and reporting of adverse and serious adverse events.

8.2.16 SWT/Sham Treatment: In the treatment group, patients randomized will receive 5 weekly sessions, in which 720 shocks of treatment energy will be applied in every session to each treated region (left and right corpora cavernosa and crura). In the sham group, patients will have the same number of sessions, and the machine will be set to deliver 720 shock treatments, but the machine will not fire shockwaves.

8.2.17 Laboratory Testing: Hematology, chemistry, hemoglobin A1C, and serum testosterone lab test results will be collected at screening. If any standard of care labs testing have been performed within 12 months of the date of the screening visit, those results may be used for the purpose of this study.

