8.3 Description of Study Visits

8.3.1 Screening Visit

Visit 1 (0 – 28 days before therapy): The basic work-up will take place, including medical and sexual history, as well as necessary lab tests (testosterone, prolactin, hematology, chemistry), if not available during the last 12 months prior to screening. Subjects will complete the IIEF questionnaire. We will ensure that patients have 4 attempts for intercourse. Screening visit can occur on same day as first injection + SWT/SHAM. Refer to table 1 for procedures to be performed at the Screening visit.

8.3.2 Treatment Visits: Week 0 – Week 4

Upon evaluation of eligibility, subjects will be randomized to one of the two parallel study groups using an online program, and initiate treatment on the same day.

There will be 5 treatment visits for all groups, each occurring at weekly intervals (± 2 days), for a total duration of five weeks. Subjects will complete a Visual Analogue Scale (VAS) pain score after the end of each treatment. Refer to table 1 for all procedures to be performed at the treatment visits.

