8.3.3 Follow Up Visits: Months 3 and 6 Post-Treatment

Follow up visits will occur within 90 ± 14 days (Month 3) and 180 ± 14 days (Month 6) days after final treatment visit. Refer to table 1 for procedures to be performed at the follow up visits visit.

9. Investigational Product

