9.2 Administration of Investigational Therapies

9.2.1 Platelet-Rich Plasma

The patient will be positioned supine. A sterile field will be developed with Betadine prep of the genitalia, sterile gloves and a sterile extremity drape. A total of 20 ml of 1% lidocaine will be drawn up using an 18-gauge needle and will be subcutaneously administered using a 27-gauge needle into the subcutaneous tissue at the base of the penis to obtain a dorsal nerve block. A 1/4-inch Penrose drain will be used as a tourniquet by placing it at the base of the penis and maintaining it in place under tension by a sterile clamp. A maximum of 5mL of PRP will be infused steadily over a two-minute period – approximately 2.5 ml each into the right and left corpus cavernosum. The infusion will be performed at this slow speed (each side over 2 minutes of infusion) to minimize injury to the platelet cells. In the control arm, men will be administered injectable normal saline that will be injected in a similar manner as the PRP.

Following administration of PRP or normal saline, compression of the penis will be achieved with a clenched fist for 20 minutes. At 20 minutes, the tourniquet will be removed, and a compressive dressing will be placed around the penile shaft. The patient will be instructed to remove the compression bandage in 4 hours and to contact the study coordinators if he experiences any problems.

Figure 1: Diagram of PRP Injection

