12.1 Adverse Events (AEs)

An adverse event (AE) is defined as any untoward medical occurrence associated with the use of a drug in humans, whether or not considered drug related. An AE can be any unfavorable and unintended sign (including an abnormal laboratory finding), symptom, or disease temporally associated with the study. The event does not need to have a causal relationship with treatment. Common Terminology Criteria for Adverse Events Version 5 (CTCAE) will be used for describing AEs. All urological and/or reproductive system AEs will be recorded. For all other AEs, only events greater than grade 2 will be recorded.

Based on our own pilot data assessing SWT and PRP monotherapy, we have compiled the following data on adverse events (Table 2):

We anticipate there to be few adverse events related to the study. Based on the four published studies and abstracts, including 75 men, only minor adverse events were reported (Bruising 1, Mild Pain 4). No serious adverse events were observed [23-26].

SWT related adverse events	
Transient mild cutaneous purpura	0.10%
Local erythema	0.50%
Local swelling/edema	1.00%
Transient local anesthesia or paranesthesia	1.10%

PPR related adverse events	
Pain greater than 5/10 at time of injection	5.00%
Pain lasting > 5 days	5.00%
Penile bruising	0.00%
Penile fracture	0.00%

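### No safety contact is scheduled for about two to three months after the second injection, and the telephone safety call in 8.2.5 has no date, so non-serious local events there depend on self-report or late recall

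*Combined protocol and SAP*

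**What the plan says.** **The call.** Section 8.2.5 reads: "Participants will be contacted by telephone to assess safety outcomes during long term follow up". It gives no day, window or number of calls. Table 1 in section 8.1 has no telephone row, 8.3 describes no call, and the last planned visit is Month 6.

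**The injections.** Table 1 marks the injection at Day 0 and at Week 5 (Day 28 ± 2), which is the last treatment visit. The synopsis and section 8 describe "2 sessions of autologous PRP penile injection with 30 ± 7 day treatment interval".

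**Adverse event review.** Table 1 marks it at Days 0, 7, 14, 21 and 28, then at Month 3 and Month 6. Table 1 places Month 3 at Day 90 ± 14 on the same day count as Day 0. Section 8.3.3 says "Follow up visits will occur within 90 ± 14 days (Month 3" and counts them as "days after final treatment visit".

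**Pain.** Section 8.3.2 says: "Subjects will complete a Visual Analogue Scale (VAS) pain score after the end of each treatment". Table 1 marks VAS at the five treatment visits only. Section 9.2.1 has lidocaine given before the injection "into the subcutaneous tissue at the base of the penis to obtain a dorsal nerve block", with saline injected in a similar manner in the control arm.

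**What is expected and recorded.** Table 2 in 12.1 includes "Pain lasting > 5 days" at 5.00% among PRP-related events. Section 12.1 also commits to recording all urological and reproductive adverse events, without a grade threshold.

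**The concern.** The two injections are followed up unequally. The first is followed within about a week by a visit with an adverse event review and a pain score. The second is followed by no scheduled contact until Month 3. The one procedure that might have covered this period, the telephone call, is promised but cannot be placed on a calendar.

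What is at stake is complete capture of non-serious local harms after half of the planned injections (60 of 120: two for each of 60 men). Many of the events anticipated in 4.1 and 15.1, such as pain, bruising, swelling, haematoma and local infection, could resolve before Month 3. Physical examination is marked at screening only, so no scheduled examination would reveal an event that the man has forgotten. In a pilot trial whose primary objective is to compare safety between arms, under-recorded local events weaken the tolerability description that a later trial would use.

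**Working it through.** **1. Gap from each injection to the next scheduled adverse event review**

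The inputs are the visit windows in Table 1, the injection interval in section 8 and the anchor in 8.3.3. The gap is the day of the next review minus the day of the injection. The shortest gap pairs the earliest review with the latest injection, and the longest does the reverse.

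| Injection and clock | Nominal | Shortest | Longest |
|---|---|---|---|
| First injection to Day 7 ± 2 | 7 | 5 | 9 |
| Second at Day 28 ± 2, Month 3 at Day 90 ± 14 | 90 − 28 = 62 | 76 − 30 = 46 | 104 − 26 = 78 |
| Second at 30 ± 7 days, Month 3 at Day 90 ± 14 | 90 − 30 = 60 | 76 − 37 = 39 | 104 − 23 = 81 |
| Second at final treatment visit, Month 3 on the 8.3.3 clock | 90 | 90 − 14 = 76 | 90 + 14 = 104 |

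Every reading leaves at least 39 days, more than five weeks, without a scheduled contact. The choice of Month 3 anchor alone moves the nominal gap by 90 − 62 = 28 days.

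**2. Whether the 8.2.5 call fills the gap**

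As written, it does not. Its only timing is long-term follow-up, which the plan never defines. Copying it into Table 1 under that label would not put it in the days after the second injection. It closes the gap only if it is given a date there.

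**3. Pain measurement**

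- The VAS scores at Weeks 2 to 4 follow shockwave or sham only.
- The VAS scores at Day 0 and Day 28 are taken at the same visit as the nerve block.
- No VAS is scheduled after the Day 28 visit.

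Injection-day VAS may therefore understate injection pain, and no VAS score can show pain that persists after the second injection.

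**4. How often prolonged pain might follow the second injection**

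Table 2 gives 5.00% with no denominator, so both readings are shown as assumptions for 30 active men.

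- *Per man over both injections, split evenly:* 0.05 / 2 = 0.025 for the second injection. Expected cases are 30 × 0.025 = 0.75. The chance of at least one is 1 − 0.975^30 = 0.53.
- *Per injection:* expected cases are 30 × 0.05 = 1.5. The chance of at least one is 1 − 0.95^30 = 0.79.

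These are chances that the event occurs, not that it goes unrecorded.

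**The case against.** The strongest reply is that no endpoint is shown to be at risk. The primary endpoint is treatment-emergent serious adverse events, defined in 12.2 and 12.3 as events such as death, hospitalization of more than 24 hours or significant disability, with a reasonable possibility of a causal link. Such events are unlikely to be forgotten by Month 3. VAS is not an endpoint at any level. Men are told in 9.2.1 to contact the coordinators with problems, 15.1 commits to systematic recording at every visit, and Month 3 includes an adverse event review. All of this stands. It limits the point to non-serious local events and makes loss a risk rather than a certainty. It does not supply a prompt, scheduled question after the second injection.

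A reader might also infer three stronger claims that the documents do not support:

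- *That the gap exists because the call was left out of Table 1.* Section 8.2.5 places the call in long-term follow-up, so scheduling it as worded would not close the gap.
- *That injection-day VAS is scored under an active block and hides excess pain with PRP.* The documents give neither the block's duration, nor the time from injection to VAS, nor the order of injection and shockwave. Understatement is plausible but not documented.
- *That there is a 79% chance of a missed case.* That figure is a chance of occurrence, and it applies to the second injection only if the 5.00% is per injection.

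**Conclusion.** The point holds as a gap in safety follow-up that is cheap to close. After the second injection the plan schedules no adverse event review for about 60 to 62 days on the Table 1 clock (39 to 81) or 90 days (76 to 104) on the 8.3.3 clock, against 5 to 9 days after the first. The 8.3.3 figures assume that the second injection is given at the final treatment visit, as Table 1 shows. The telephone safety call is promised but undated.

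The consequence is incomplete or late capture of non-serious local events that the plan says it will record. The TE-SAE endpoint is little affected. For prolonged pain after the second injection, the plan's rate implies about 0.75 to 1.5 of 30 active men, depending on the assumed denominator. The gap and the missing date are plain on the text. The effect of the nerve block on VAS is an inference.

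**What to change.** - Enter the 8.2.5 call in Table 1 and in 8.3, with a date and window about 7 days after the second injection, to mirror the Day 7 contact after the first.
- Script the call. It should ask about each anticipated event in 4.1 and 15.1 and include a pain item: worst pain since the injection, and whether pain lasted more than 5 days.
- Ask the same pain item at the existing Day 7 visit, so that both injections are assessed alike.
- Report injection-day VAS as taken at the same visit as a local anaesthetic block.
- Define long-term follow-up or delete the term.
- Reconcile the Month 3 anchor (Table 1 against 8.3.3) and the second-injection timing (Day 28 ± 2 against 30 ± 7 days).

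The cost is about 60 short calls of coordinator time, one pain item added to an existing visit, and one row in Table 1 with matching text in 8.3.
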